6.2 Assignment

Participants will be randomized individually to 1 of the 2 arms using REDCap randomization module, stratified by three conditions: 1) medication status (new or prevalent starts), 2) drug class (ALK vs ROS1), and 3) study hospital (PCAM vs PPMC). Enrolled patients will learn their assignment (open label) following completion of the baseline survey.

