5.4 Target Population

Aim 1. The study aims to enroll 170 adult patients (18 years or older) with advanced NSCLC who have initiated oral targeted therapies at UPHS. These include afatinib, erlotinib, dacomitinib, gefitinib and osimertinib for patients harboring sensitizing EGFR mutations; and alectinib, brigatinib,, crizotinib, and lorlatinib for patients with anaplastic lymphoma kinase (ALK) or ROS1 rearrangements. To be eligible, participants must be receiving ongoing cancer care at a participating site; have access to a mobile phone with SMS text messaging capabilities; be able to read and respond to questions in English; and must have started taking oral targeted therapies no earlier than January 1, 2020 and no later than the end of study recruitment (estimated October 2021).

Aim 2. The study aims to interview 30-45 patients and 15-30 clinicians. Patients will be eligible if they are enrolled in the intervention trial (Aim 1). Clinicians will be eligible if they actively provide care for cancer patients on targeted oral therapies at one of the study sites (including but not limited to oncologists, advanced practice providers, triage nurses, and pharmacists).

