5.5 Sample Size and Accrual

Aim 1. The study sample will be drawn from adults seeking cancer care at the University of Pennsylvania's Abramson Cancer Center (ACC). Across recruitment sites, approximately 215 patients with lung cancer had orders for one of the included oral targeted therapies from January-September 2020. For this study, we will include both patients who have new prescriptions (after study launch) and patients previously taking these medications in 2020 (and who continue to take these medications at the time of eligibility assessment). Based on preliminary studies with Penny, we conservatively estimate that $\geq 40\%$ of patients approached will be eligible and consent to participate in this study. Of the 215 patients who started taking these medications in 2020 and estimated number of new starts during the study enrollment period (estimated 25 new starts per month), we anticipate that we will reach our target sample size of 170 in approximately 9-12 months (enrolling an estimated 85 patients who are currently taking these medications and 10 patients monthly who are new medication starts across the enrollment period). Allowing for a 15% loss to follow up, 72 participants will remain in each arm ($n=144$). Our full sample will provide 80% power to detect minimum effect of 20.9% or greater between the intervention and control group (assuming previously observed 65.5% adherence rate in controls and using fisher's exact test⁷), an effect size that is clinically significant and appropriate for this pilot stage of research.

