5.6 Key Inclusion and Exclusion Criteria

Aim 1: Trial Participants

Inclusion Criteria

- Adult patient (age > 18 years) with advanced NSCLC at UPHS who is receiving one of the following nine oral therapies: afatinib, erlotinib, dacomitinib, gefitinib, osimertinib, alectinib, brigatinib, crizotinib, or lorlatinib.
- Patient possession of a mobile device that can send/receive SMS texts
- Ability to respond to questions and engage with “Penny” in English
- Ability to provide informed consent to participate in the study
- Blanket approval from the patient’s medical oncology to be approached

Exclusion Criteria

- Inability to respond to questions and engage with “Penny” in English
- Inability or unwillingness to provide informed consent to participate in the study
- Inability to engage with SMS text-messaging platform
- Concurrent enrollment in a therapeutic clinical trial
- Lack of blanket approval from the patient’s oncologist

Aim 2: Interview Participants: Patients

Inclusion Criteria

- Adult patient who consented and enrolled in the intervention trial (Aim 1)
- Ability to respond to interview questions in English
- Ability to provide informed consent to participate in the study

Exclusion Criteria

- Did not meet eligibility criteria to enroll in the intervention trial (Aim 1)
- Inability to respond to interview questions in English
- Inability to provide informed consent to participate in the study

Aim 2: Interview Participants: Clinicians

Inclusion Criteria

- Clinician employed by UPHS who routinely provides care for cancer patients on targeted oral therapies at one of the recruiting study sites including but not limited to oncologists, advanced practice providers, triage nurses, and pharmacists.
- Ability to respond to interview questions in English
- Ability to provide informed consent to participate in the study

Exclusion Criteria

- Does not provide routine care for cancer patients on oral targeted therapies at UPHS
- Inability to respond to interview questions in English
- Inability to provide informed consent to participate in the study

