9. ANALYSIS PLAN

9.1 Primary Analyses

Our primary analyses will use an intent-to-treat (ITT) approach using repeated measures logistic regression to compare the overall effect of the intervention on patient adherence. We will also explore potential differences in secondary outcomes across arms. Baseline clinical and survey data will be used

to assess potential differences in treatment groups (i.e., socio-demographics and clinical risk factors) using parametric or nonparametric tests as appropriate. Data quality, normality, and other assumptions will be assessed prior to analysis. Using repeated measures logistic regression fitted using generalized estimating equations (GEE), we will compare the proportion of adherent days between Penny and usual care. Data will be treated as binary outcome (0/1) over the study period. Models will contain a predictor term for treatment arm, will be adjusted for time (discrete week), and will contain subject specific random effects and fixed effects for site. Patients will be categorized as adherent (outcome=1) across the study period if the total percentage of adherent days is $\geq 95\%$ similar to previous studies⁷; other percentages (80%, 90%, 100%) will be explored in sensitivity analyses. Persistence will be treated as repeated measure survival data and will be summarized as median survival time using Kaplan-Meier methods. We will also generate summary statistics (including mean adherence rate) to help describe the study population and inform the design of further studies.

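### The drug-class stratification factor in section 6.2 (ALK vs ROS1) has no level for the EGFR patients whom sections 5.4 and 5.6 make eligible

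*Combined protocol and SAP*

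**What the plan says.** Section 6.2 states that patients are randomised individually through the REDCap module, with three stratification factors. The first is medication status; the other two are given as "2) drug class (ALK vs ROS1), and 3) study hospital (PCAM vs PPMC". The drug-class factor therefore has two levels, ALK and ROS1, with no EGFR level and no residual category.

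Section 5.6 defines eligibility by drug, not by mutation: the patient must be "receiving one of the following nine oral therapies: afatinib, erlotinib, dacomitinib, gefitinib, osimertinib, alectinib, brigatinib, crizotinib, or lorlatinib". The protocol summary (section 1) gives the same nine. Section 5.4 links drug to mutation. For the first group it says: "These include afatinib, erlotinib, dacomitinib, gefitinib and osimertinib for patients harboring sensitizing EGFR mutations". The remaining four drugs form one shared list, which ends "crizotinib, and lorlatinib for patients with anaplastic lymphoma kinase (ALK) or ROS1 rearrangements".

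In section 9.1 the primary model has terms for arm and week and "will contain subject specific random effects and fixed effects for site". Hospital is thus the only stratification factor named in the model.

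**The concern.** The levels of a stratification factor have to cover every patient who can be randomised, and each patient has to fall in exactly one level. This factor fails the first requirement for EGFR patients. It is also unclear on the second for the rest: section 5.4 does not divide its four ALK/ROS1 drugs between the two rearrangements, so a level cannot be read from the drug alone.

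This is an operative allocation rule, not background text. If REDCap was set up as section 6.2 reads, staff must either leave EGFR patients unplaced or enter them under a level that does not describe them. If different staff chose differently, the stratification would no longer balance the arms on drug class. What is at stake is chance balance on one covariate and a description of the randomisation that others could reproduce. The size of the trial and the unbiasedness of the arm comparison are not at stake.

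**Working it through.** **1. Coverage of the factor**

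| Group in 5.4 | Eligible drugs (5.4, 5.6) | Level in 6.2 |
|---|---|---|
| EGFR | afatinib, erlotinib, dacomitinib, gefitinib, osimertinib (5) | none |
| ALK or ROS1 | alectinib, brigatinib, crizotinib, lorlatinib (4) | ALK or ROS1; drugs not mapped to one or the other |

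Five of the nine eligible drugs have no level. No other section redefines the factor or says how EGFR patients are placed.

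**2. The plan's own figure**

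The yardstick for any effect on the estimate is the detectable difference in section 5.5. With 65.5% adherence in controls, 65.5% + 20.9% = 86.4% in the intervention arm, 72 evaluable patients per arm (170 × 0.85 / 2 = 72.25) and Fisher's exact test, exact enumeration gives power of 80.03%. Two-sided alpha of 0.05 is assumed, because the section states neither alpha nor sidedness. This reproduces the stated 80%. The figure does not depend on the stratification.

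**3. Patients without a level**

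The documents do not give the EGFR share p, so it is assumed over a range: 170 × 0.5 = 85, 170 × 0.7 = 119, 170 × 0.9 = 153.

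**4. Chance imbalance if drug class plays no part in allocation**

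With 85 patients per arm, the SD of the between-arm difference in EGFR share is √(4p(1−p)/170). For the exact calculation, the number of EGFR patients in one arm is X ~ Hypergeometric(170, N, 85), where N is the total number of EGFR patients. The event is |2X − N|/85 ≥ 0.10.

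| Assumed p | N | SD | P(imbalance ≥ 10 points), normal | Same, exact |
|---|---|---|---|---|
| 0.5 | 85 | 0.077 | 0.192 | 0.220 |
| 0.7 | 119 | 0.070 | 0.155 | 0.180 |
| 0.9 | 153 | 0.046 | 0.030 | 0.038 |

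The risk falls as the EGFR share rises.

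**5. Effect on the unadjusted arm difference**

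Shift = imbalance × difference in adherence between drug classes. The class difference is not in the documents and is assumed at 5, 10 or 20 points:

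- 0.10 × 5 = 0.5 points (0.5/20.9 = 2% of the detectable difference)
- 0.10 × 10 = 1.0 point (5%)
- 0.10 × 20 = 2.0 points (10%)

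**6. Strata under each possible repair**

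- EGFR vs ALK/ROS1: 2 × 2 × 2 = 8 strata, 170/8 = 21.3 patients on average.
- EGFR, ALK and ROS1: 2 × 3 × 2 = 12 strata, 170/12 = 14.2 on average.

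These are averages only. The documents give no distribution over the factors, and real strata may be very unequal.

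**The case against.** The strongest reply is that this is a slip of wording with little consequence. Section 5.4 sorts the nine drugs into exactly two groups, section 6.2 gives the factor exactly two levels, and EGFR vs ALK/ROS1 would fit both. The REDCap set-up is not in the documents, so nothing shows that any patient was misplaced. If every EGFR patient was entered in one level and every ALK/ROS1 patient in the other, balance would hold whatever the levels were called. Stratifying on drug class is not needed for validity, and the imbalance figures rest on an assumed EGFR share. Section 9.1 also plans a baseline comparison of the arms, and section 8.3 collects tumour and treatment details. An imbalance could therefore be seen and described, and rearrangement type could perhaps be taken from the record.

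Most of this stands as a limit on weight. The consequence is small, the only firm count is five of nine drugs, and no fault in conduct has been shown. It does not remove the inconsistency. Two repairs fit the text and give different allocation schemes, and only the sponsor can say which was meant. A later baseline table can describe an imbalance but does not supply the balance by design that section 6.2 sets out to secure.

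**Conclusion.** The concern holds. Section 6.2 cannot be carried out as written for patients on five of the nine eligible drugs, and it contradicts sections 5.4 and 5.6 read together (5.6 names the drugs; 5.4 supplies the link to EGFR). Confidence is high for the inconsistency in the text. Whether it had any effect in practice cannot be judged without the REDCap configuration.

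The statistical consequence is modest. Power, 1:1 random allocation and the validity of the comparison are untouched. The probabilities of 22%, 18% and 4% rest on assumed EGFR shares of 50%, 70% and 90% and on drug class having no influence on allocation. The shift of 0.5 to 2 points also needs a 10-point imbalance and an assumed adherence gap of 5 to 20 points between classes. It should be fixed because it is an allocation rule and the correction costs almost nothing, not because the primary result is threatened.

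**What to change.** In section 6.2, replace the drug-class levels with the groups used in section 5.4: EGFR-directed vs ALK/ROS1-directed therapy. This keeps eight strata. If the sponsor meant to keep ALK and ROS1 apart, use three levels (EGFR, ALK, ROS1), which adds four strata, and say how a patient is assigned to ALK or ROS1. The sponsor should state which was intended and confirm that the REDCap field matches.

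Before randomisation starts, this costs one line of protocol text and a check of one field, with no additional patients. If enrolment has begun, it also needs a dated note on how patients already randomised were coded and how any change was made.

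Separately and optionally, add the corrected drug-class factor and medication status to the primary model in section 9.1 alongside site, so that the analysis reflects all the stratification factors.

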6.3 Blinding

Co-investigators and the primary statistician and analyst will be blinded to the randomization assignment. The clinical research team, PIs, and patients will be unblinded given the nature of study monitoring and intervention. The clinical research coordinator will record the randomization assignments on a master list and enter into REDCap using the randomization module. Assignments will be maintained by the research coordinator on a password protected computer in a locked office. The blind may be broken in the case of an emergency.

7. STUDY PROCEDURES

7.1 Eligibility Screening and Recruitment

Aim 1. Potentially eligible participants will be identified in one of three ways: (1) direct referral from inpatient or outpatient medical oncology teams, (2) manual chart review by research staff of new medication orders; and (3) extraction of eligible patients from Clarity based on the inclusion criteria listed above. Due to COVID-19, potentially eligible patients will be approached by a member of the clinical research team by phone; study introduction will only be conducted in person if allowable by research resumption guidelines. A member of the study team will attempt to contact the identified patient up to three times by phone to assess interest (recruitment script included in the protocol). During the screening phone call, if the patient expresses interest in the study, the study team member will ask the patient to provide contact information and preferred day and time to schedule a follow-up phone call to discuss informed consent. The study team member will also add a note to the patient's medical record noting the patient has been approached and if the patient agreed or not to be contacted

further about the study. Prior to study launch, all medical oncologists in the lung cancer program at Penn will be notified of the study and asked for blanket approval to contact their patients if eligible.

Aim 2. For patient interviews, enrolled patients in the intervention trial will be purposively sampled by study arm, race and age, and adherence outcome (in batches of 15) to participate in a one-time interview approximately 2 weeks after the completion of active intervention. As part of the trial consent process, patients who enroll in the trial will be notified that a subsample will be approached for this secondary component of the study. At the time of trial completion, a research coordinator will contact the sampled patients via phone to assess interest in participating in the interview. If patients are interested, they will be scheduled for an in-person or phone interview at their convenience. Research coordinators will attempt to contact patients no more than three times via phone to assess interest, following which patients will not be contacted further. For clinician interviews, the PIs will reach out to clinicians in ACC via blanket email following completion of the trial. The email will describe the general scope of the study and eligibility criteria and ask providers to respond if they are interested in participating. We will also directly reach out to individual providers we believe are eligible based on clinical relationships to assess interest, and also use snowball sampling to identify additional providers following enrollment of first providers.

7.2 Consent and Enrollment

Aim 1: Consent Discussion (Trial participants): If a patient expresses interest in participating following the study introduction, the patient will be contacted by phone to have a consent discussion in accordance with Penn Medicine remote consent procedures. During the consent discussion, we will discuss the voluntary nature of the study, risks and benefits of participation, randomization, and answer any questions that the participant may have. We will discuss the potential accessibility of patients' health information by a third party, Memora Health, for withdrawal of specific data points necessary for the development and programming of "Penny" (name, drug type, prescription, contact information). We will ask patients to verbally confirm willingness to participate or decline participation.

Aim 1: Documentation of Consent (Trial participants): For those participants who verbally confirm willingness to participate during the consent discussion, we will use REDCap to document consent as recommended by Penn Medicine remote consent procedures. The individualize REDCap link will include the full informed consent form and ask participants to document consent and understanding prior to proceeding to the baseline survey. We will also mail and/or email participants a copy of the informed consent form (included in this protocol) that will include information on how to contact the research team via email or phone if they have study related questions, concerns or choose to withdrawal from the study at any time. Only participants who document consent and complete the baseline survey will be randomized and included in this study.

Aim 2: Verbal Consent & Waiver of Written Consent (Interview participants only): For patient and clinician interviews, the consent process will be separate from the consent process for the trial. Interview participants will be asked to provide verbal consent prior to commencement of the interview. The verbal consent discussion will describe the potential benefits and risk of participating in the interview and provide information on referral resources should they experience any discomfort or concern from participation. Due to COVID restrictions, we anticipate the vast majority if not all interviews will be conducted via telephone. Therefore, we are requesting a waiver of written documentation of informed consent. Interviews present no more than minimal risk of harm and involve no procedure for which written consent is normally required. The written consent form would be the only record linking the participant with the interview data. Consent statements will be provided via email to participants prior to the interview and also reviewed verbally at the time of the interview. Verbal consent forms and recruitment scripts for patient and clinician interviews will be submitted for IRB review prior to commencement of interviews.

8. DATA MANAGEMENT

8.1 Data Collection

This study is staffed by a research support team that includes a data manager and statistical analyst who will have direct access to study data. Additional study staff (project manager, research coordinators, investigators) will have access to patients' contact information in order to coordinate study activities. Access to all study data will be limited to specifically designated researchers.

8.2 Assessment Procedures

MEMS Caps. Adherence data will be assessed via MEMS caps, which capture a date and time stamp each time the pill bottle is opened. MEMS caps are considered the gold standard of objective adherence measurement over other methods of adherence monitoring,^{31,32} and have been used successfully in previous studies of oral anticancer agents.^{5,25} MEMS data will be scanned to a secure web portal by research staff at the time of clinic appointments. All participants will receive MEMS cap(s) regardless of study assignment. Participants will be instructed to use this system for storage throughout the study, and to log any bottle openings for purposes other than pill ingestion (e.g., to check remaining supply) in a daily journal. After patients complete the baseline survey, a study team member will mail the MEMS Caps directly to the patients with instructions on how to install the MEMS cap. Patients will be contacted by phone approximately 7-10 days after the MEMS cap is mailed to them to confirm receipt and answer any questions. Patients will be instructed to begin using the MEMS cap the day immediately following the phone call as this will be their study start date.

Online Surveys. Trial participants (Aim 1) will be asked to complete online surveys at three timepoints: baseline assessment (T0) will occur at time of enrollment, followed by mid-point assessment approximately 6 weeks later (T1), and final assessment occurring within 2 weeks of trial completion (T2). Data will be captured via REDCap, a secure, web-based application for collecting and managing survey data³³. For REDCap data, patients will receive individualized links to each survey and will be contacted up to three times by email, text message, and/or phone to complete each survey. To increase data completion and study retention incremental compensation will be provided to patients. Specific measures to be assessed in the survey are described below.

Medical Record Data: Medical record data from enrolled patients will be abstracted across the study period to evaluate diagnostic and treatment changes, clinical characteristics, and healthcare utilization. We will also use medical record data to identify and recruit potentially eligible patients as outline in the HIPAA waiver.

Interviews (Aim 2). *Patient Interviews:* A semi-structured guide including open- and closed-questions informed by the Information-Motivation-Behavioral Skills (IMB) model will be used to a) examine patient experiences including barriers and facilitators to medication adherence; b) assess usability and acceptability of Penny as part of care; c) explore the potential impact of Penny or other strategies on medication adherence, self-efficacy, and symptom management; and d) gather additional feedback on how Penny could be improved to help support care. *Clinician Interviews.* At the beginning of all clinician interviews, clinicians will be given a synopsis of Penny (how it works, what it aims to do, and preliminary outcomes from pilot testing), and shown an informational video to serve as a stimulus for the interview. A semi-structured guide including open- and closed-ended questions will be used to explore a) feasibility, acceptability, and potential impact of using Penny to improve medication adherence, symptom management, and other cancer outcomes; b) how various factors may shape integration of Penny into routine cancer care, drawing from the five domains in the Consolidated Framework for Implementation Research (CFIR); c) standard of care provided to patients on targeted therapies; and d) clinician characteristics. Both patient and clinician interview participants will also complete a structured questionnaire prior to the interview to assess closed-ended questions related to

medication beliefs and practices and perceived usefulness and ease of use of Penny. A copy of the final patient and clinician interview guide will be submitted for IRB review prior to interview commencement.

Interviews will last 30-45 minutes and will be supervised by [name], who has extensive experience conducting interviews with clinicians and patients. Interviews will take place in a private setting or via phone (based on participant preference and research resumption guidelines). Structured questionnaires will be administered verbally or online (using REDCap) prior to the interview. Interviews will be audio-recorded and transcribed verbatim using a HIPAA-compliant transcription company.

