Exploratory Outcomes. Across the intervention study, we will quantitatively assess patient-reported outcomes at various time-points to reduce burden and capture longitudinal changes. Specifically, we will measure medication beliefs and practices³⁹, health-related quality of life (HRQOL),³⁷ symptom burden,^{38,39} patient satisfaction,⁴⁰ financial toxicity,⁴¹ social and behavioral determinants of health (SBDH),⁴² medication self-efficacy,⁴⁷ patient-provider communication, and health literacy.⁴⁰ HRQOL will be measured using the EuroQol EQ-5D, a 5-item index that assesses mobility, self-care, pain, usual activities, and anxiety/depression, and provides a composite score of general HRQOL.³⁷ Symptom Burden will be measured using the Edmonton Symptom Assessment Scale (ESAS).^{42, 43} Patient Satisfaction will be measured by a single item measuring overall patient satisfaction from FACIT-TS-PS, a validated survey.⁴⁰ Financial Toxicity will be measured using the 11-item Comprehensive Score for financial Toxicity (COST) instrument, developed to assess financial toxicity in patients with cancer.⁴¹ SBDH will be assessed by a validated panel of measures recommended by the Institute of Medicine.⁴² Medication self-efficacy will be measured by the 13-item Self-Efficacy for Appropriate Medication Use Scale (SEAMS), which has been validated for this purpose.^{43,44} Patients in the intervention arm will also assess usability using the Health Information Technology Usability Evaluation Scale (Health-ITUES). Lastly, we will capture impact of COVID on patient experiences and care. Clinical characteristics (tumor and treatment specifics), acute care utilization (emergency room and hospital admission), and mortality will be measured as count variables across the study period using EMR data and also patient self-report to capture any visits outside our healthcare system. Prior to study launch, we pilot tested the survey measures to assess participant burden and reduced. All final survey items are included in the Appendices.

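### As Section 8.2 is written, clinicians and usual-care patients would rate the usefulness and ease of use of Penny without any described exposure to it

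*Combined protocol and SAP*

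**What the plan says.** Section 8.2 (Interviews, Aim 2) fixes the timing of the structured questionnaire twice: "Both patient and clinician interview participants will also complete a structured questionnaire prior to the interview", and "Structured questionnaires will be administered verbally or online (using REDCap) prior to the interview". Its content is "medication beliefs and practices and perceived usefulness and ease of use of Penny".

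For clinicians, the same section says "At the beginning of all clinician interviews, clinicians will be given a synopsis of Penny", followed by an informational video that is to serve as the stimulus. The clinician guide comes after that: "A semi-structured guide including open- and closed-ended questions will be used to explore a) feasibility, acceptability, and potential impact of using Penny".

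For patients, Section 7.1 says that "enrolled patients in the intervention trial will be purposively sampled by study arm, race and age, and adherence outcome", and Section 5.5 also lists study arm among the sampling variables. Under Section 5.6, any patient enrolled in the trial may be interviewed. One topic of the patient guide is to "assess usability and acceptability of Penny as part of care". Section 8.2 describes no demonstration of Penny for patients.

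Section 8.3 treats a different usability instrument differently: "Patients in the intervention arm will also assess usability using the Health Information Technology Usability Evaluation Scale". Section 9.3 says only that survey data are analysed descriptively and triangulated with the qualitative data.

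**The concern.** A rating of ease of use carries information when the respondent has used the tool or has at least been shown it. In the written sequence, two groups may have had neither. Clinicians answer before the material that the protocol itself supplies as the stimulus. Usual-care patients answer about a program that was not part of their care.

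Aim 2 is one of the trial's two specific aims and is directed at acceptability, effectiveness and future implementation. The questionnaire ratings are to be set beside the interviews. If a clinician's ratings come before the demonstration and the interview follows it, a disagreement between the two may reflect only the order of the steps. Ratings collected too early cannot be corrected afterwards.

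**Working it through.** The plan gives no figure for this point, so there is none to reproduce. The check is one of sequence and exposure, followed by simple arithmetic for scale.

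**Step 1. Order of steps for clinicians.** Section 8.2 gives: (i) questionnaire, including the Penny items; (ii) interview opens with synopsis and video; (iii) guide questions, including acceptability. Step (i) precedes (ii). Section 5.3 lists the session as consent, interview and then a written questionnaire. That is a list rather than an explicit sequence, but it puts the questionnaire last and calls it written, whereas Section 8.2 puts it first and makes it verbal or online. The two sections do not agree.

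**Step 2. Could clinicians know Penny already?** Possible routes are the notice to lung medical oncologists before launch (7.1), the triage of severe side effects to care teams (6.1) and the recruitment email giving the study's general scope (7.1). None is a described demonstration. Eligibility (5.5, 5.6) requires only that the clinician cares for patients on these drugs. Prior exposure is therefore possible but not assured.

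**Step 3. Exposure of patients.**

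| Group | Access to Penny in the trial | Penny items restricted? |
|---|---|---|
| Intervention arm | About 12 weeks (6.1) | Not needed |
| Usual care | None; standard care only (6.1) | No restriction stated (8.2) |

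That usual-care patients receive the Penny items follows from the absence of a restriction, not from an explicit statement.

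**Step 4. Scale.** Let P be interviewed patients, C clinicians, f the fraction of P from usual care, and u the fraction of C with no earlier exposure. The share of questionnaires affected is (f·P + u·C)/(P + C). Sections 5.4 and 5.5 give P = 30-45 and C = 15-30; the Protocol Summary, 4.1 and 5.1 give 30 and 30. The documents state neither f nor u. Assume f = 1/2 (15 of 30, or 22 of 45 rounded down).

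| P | C | u = 1 | u = 0 |
|---|---|---|---|
| 30 | 15 | (15 + 15)/45 = 67% | 15/45 = 33% |
| 45 | 30 | (22 + 30)/75 = 69% | 22/75 = 29% |
| 45 | 15 | (22 + 15)/60 = 62% | 22/60 = 37% |
| 30 | 30 | (15 + 30)/60 = 75% | 15/60 = 25% |

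With equal arms, the share is 62-75% if no clinician has met Penny and 25-37% if all have.

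**The case against.** The strongest reply is that acceptability is not what this questionnaire is assigned to measure. It asks about perceived usefulness and ease of use. Acceptability is placed in the interview guides, which include closed questions and which, for clinicians, follow the synopsis and video. Intervention-arm patients have lived with Penny for about 12 weeks, and Health-ITUES already provides a usability measure limited to users. A reader might infer from the sequence that the Aim 2 acceptability ratings as a whole fail to measure acceptability. The documents do not support that, for these reasons.

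A reader might also infer that ratings from exposed and unexposed respondents will be pooled. Section 9.3 states neither pooling nor separation, and arm and role are known for every respondent.

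Further, the Aim 2 questionnaire items cannot be seen, so skip rules or arm-specific wording cannot be excluded. A semi-structured guide lets an interviewer leave out topics that do not fit. Because Aim 2 looks to future implementation, the views of people who have not used Penny are relevant, and usual-care patients heard about the study in the consent discussion (7.2).

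All of this narrows the point. It does not remove it. Section 8.2 states the clinician order twice, and no described step exposes clinicians to Penny before they rate it. A usual-care patient can hold a view on whether such a tool would be useful, but has no experience from which to rate its ease of use.

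**Conclusion.** The point holds in a limited form. Followed as written, Section 8.2 collects usefulness and ease-of-use ratings from clinicians before the study introduces Penny to them. Because no arm restriction is stated, it also collects them from usual-care patients, who were not given the tool. The clinician part rests on the stated sequence. The usual-care part rests on the missing restriction, and skip rules in the unseen items could change it.

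The affected share is at most about 62-75% if the arms are equally represented and every clinician is unexposed. Both conditions are assumptions, and any earlier clinician exposure lowers the figure. The consequence is confined to one descriptive component of Aim 2. The Aim 1 primary and secondary outcomes do not depend on it.

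**What to change.** 1. **Section 8.2, clinicians:** keep the items on medication beliefs and practices before the interview. Move the Penny items to after the synopsis and video and before the guide questions.
2. **Section 8.2, patients:** limit use-based Penny items to the intervention arm. Ask usual-care patients only about anticipated usefulness, after a short description of Penny.
3. **Sections 5.3 and 8.2:** state one order and one mode for the questionnaire.
4. **Section 9.3:** report the ratings separately for intervention-arm patients, usual-care patients and clinicians. Recording whether each clinician had met Penny before would allow the clinician ratings to be read by exposure.

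The cost is a reordered questionnaire, branching by arm in REDCap, a short description for usual-care patients and a few sentences of text. Section 8.2 says that the final interview guides are still to go to the IRB before interviews begin, so the change can go in with that submission. Sample size and the Aim 1 procedures are unchanged.
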